7.5.5 Exploratory Efficacy Analyses

None of the exploratory endpoints will be statistically tested.

7.5.5.1 Mean change from baseline at Week t

The analyses of change from baseline in exploratory endpoints will be performed using the longitudinal repeated measures model (Model 7.1.2.1, including the stratification factor) as described in Section 7.1.2.

7.5.5.2 Glycemic Rescue or Discontinuation from Study treatment due to Lack of Efficacy

The proportion of subjects requiring treatment intensification (glycemic rescue or discontinue study treatment for lack of efficacy) up to Week 24 / 52 will be assessed by summarizing the difference in the percentages between treatment groups and by a time-to-event analysis using the Kaplan-Meier methodology.

Time to treatment intensification will be analyzed using a Cox proportional hazards model. Estimates of hazard ratio and 95% confidence intervals will be provided. Kaplan-Meier plots^{□1} of time to intensification at Weeks 24 and 52 will be calculated and plotted by treatment group. Unless otherwise specified, the plot will be presented only when there are at least 10 events in one treatment group. Additionally, a table will accompany the plot and will display the Kaplan-Meier estimates of the cumulative proportion (with 95% CI calculated based on Greenwood's method^{□2} when applicable) of subjects with event at specific time points by treatment group. If the estimated lower bound of 95% CI is below 0 or the estimated upper bound of 95% CI is over 1, then it will be restricted to 0 or 1 respectively. For the analysis during 24 / 52 weeks, all subjects will be censored at Week 24 / 52 visit (end of ST treatment/end of LT treatment) if treatment intensification has not occurred by then. Subjects rescued at Week 24 / 52 will be counted as having an event for the analysis.

Composite response endpoints (glycemic control without hypoglycemia), will be analyzed using logistic regression with adjustment for baseline HbA1c value and/or the stratification factor. None of the exploratory endpoints will be statistically tested

In addition, an analysis of the proportion of subjects not rescued and achieving glycemic response (defined as HbA1c < 7%) in subjects from the Short-term Completers Data Set at time points during the LT period will be performed using the same methodology described above (with adjustment for end of ST HbA1c measurement). Subjects discontinued or missed measurements (regardless of the type of missing) at the specific time point will be considered as not achieving glycemic response.

7.5.5.3 Summary of change from baseline for lipids

The change from baseline in lipids data during the short-term and long-term treatment periods will be summarized for each treatment group.

7.5.6 Summary of Primary Efficacy Endpoint within Subgroups

Treatment effects will be assessed for subgroups based on age group, gender, race, region, and baseline HbA1c, as defined in Table 7.3.2A and Table 7.3.2B. The analyses will be based on model 7.1.2.1 with additional covariates of subgroups, treatment-by-subgroup, visit-by-subgroup, and treatment-by-visit-by-subgroup. Additionally the treatment-by-stratification interaction will be assessed. The nominal p-value for subgroup-by-treatment interaction will be presented. The p-value for the test of treatment by age, female age, baseline HbA1c, and baseline eGFR interaction will include corresponding continuous subgroup variables in the model.

Adjusted mean change from baseline and its difference from the control group will be given for each subgroup at week 24.

7.5.7 Pharmacokinetic Analyses

Not applicable

7.5.8 Biomarker Analyses

Not applicable.

7.5.9 Outcomes Research Analyses

The Phase V® Health Outcomes Information System Diabetes Module will be used for the patient-reported outcomes (PRO) assessments. The self-administered PRO questionnaires consist of validated generic and diabetes-specific modules of treatment satisfaction, quality of life, barriers to medication adherence and weight perception. Mean change from baseline in these parameters will be analyzed using longitudinal repeated measures model with terms for treatment group, baseline value, randomization stratification factor (back ground medication of metformin alone vs. metformin + SU), time, the interaction of treatment and time, and the interaction of baseline value and time. Point estimates and 95% confidence intervals will be calculated for the adjusted mean changes within each treatment group as well as for the differences in adjusted mean changes between treatment groups.

Phase V® is collecting the data and analyzing the data for patient reported outcomes in this study. More details on the collection and analysis is provided in Appendix 2.

7.5.10 Other Analysis

Not applicable.

7.5.11 Interim Analyses

There will be produced one study report at the end of Short-term Period and a second study report at the end of Short-term plus Long-term period.

7.6 Safety

The assessment of safety will be based on the analyses of AEs, vital signs, physical examinations, ECGs, hypoglycaemia, and clinical laboratory evaluations. All safety analyses will be performed using treated subjects data set.

The Treated Subjects Data Set will be used for all safety analyses, including data after rescue. Safety analyses will be performed using data from the 24-week open label period (at the time of the primary endpoint analysis) and then again at the final database lock (52 weeks) on the combined ST+LT treatment period. Sensitivity analyses on data collected prior to rescue will be performed for selected Adverse Events (AEs) as described in Section 7.6 of the ST Core SAP and Section 7.5 of the ST+LT Core SAP.

7.6.1 Adverse Events

Adverse events analyses will be performed for the ST and ST+LT periods.

Adverse Events (AEs) will be classified by Primary System Organ Class (SOC) and Preferred Term (PT) according to the Medical Dictionary for Regulatory Activities (MedDRA). Summaries of AEs will use the version of MedDRA that is current at the time of database lock for each study. Counting rules for adverse events are described in Section 8.7.

In summaries by SOC and PT, AEs will be sorted by decreasing frequency within each SOC and PT. In summaries by PT, AEs will be sorted by decreasing frequency within PT according to the highest of either of the combinational dose group across the study.

Separate pages to capture events of hypoglycemia are contained within the CRF. Hypoglycemia or discontinuation due to hypoglycemia would not be reported on an AE CRF page unless the event fulfilled criteria for a Serious AE (SAE) in which case an SAE form would be completed. Hypoglycemia events that are reported as SAEs will be included in all summaries of AEs or SAEs (see Section 7.6.1.1). Separate summaries will be provided including hypoglycemia events reported on that special CRF pages.

7.6.1.1 All Adverse Events

An overall summary of adverse events at subject level, including AEs, SAEs, death, hypoglycemia, treatment-related events and events leading to the discontinuation of study medication will be performed for the short-term treatment periods. All adverse events (serious and non-serious, excluding hypoglycemic events that are not reported as SAEs) will be summarized by system organ class, preferred term for the short-term treatment periods. For the analyses of the short-term treatment period, the summary of AEs and analyses by SOC and PT will be performed for the primary and sensitivity safety analyses. In addition, a subject listing of all reported adverse events will be produced, displaying all events (including pre-treatment events) that occurred prior to the start date of long-term treatment period, if any. All adverse events (serious and non-serious) including all hypoglycemic events will also be summarized by treatment group, where applicable.

AEs and SAEs with an onset from Day 1 of short-term treatment up to and including 4 days and 30 days respectively, after the last dose date in the short-term treatment period (or up and including to the start date of the long-term treatment period whichever comes first) will be considered as occurring during the short-term treatment period.

In addition, the following summaries will be provided for the short-term treatment period (excluding hypoglycemic events that are not reported as SAEs):

- Most common adverse events by preferred term and treatment group (i.e., reported by ≥ 2 % of subjects in any treatment group),
- Adverse events by system organ class, preferred term, intensity and treatment group,

- Adverse events related to study medication by system organ class, preferred term and treatment group.
- Proportion of subjects with adverse events by SOC and PT in subgroups of subjects defined by age category (< 65 and ≥ 65 yrs), gender, race, and female age category (≤ 50 and > 50 yrs).

In addition to analyses of event incidence at the subject level, recurrence analyses will be performed at the event level. In order to prepare these summaries, the CRF data will be processed to categorize each line of patient data as a new occurrence or a continuation of an existing event. This determination will be based upon onset and resolution dates. Each line of patient data will represent the maximum severity observed at the time of occurrence as well as the last known assessed relationship to study medication by the investigator.

The following summary information will be provided:

Total number and rate (exposure adjusted) of occurrences for all AEs occurring in at least 5% of the subjects treated.

Additionally, a listing will be provided displaying the unique instances of all AEs, i.e., after duplicates have been eliminated and overlapping and contiguous occurrences of the same event have been collapsed. Because of how hypoglycemic events are assessed and captured in the database, each reported event is assumed to be unique and multiple hypoglycemic events will not be collapsed.

Similar analyses of adverse events will be performed for ST+LT treatment period. AEs and SAEs with an onset from Day 1 of short-term treatment up to and including 4 days and 30 days respectively, after the last dose date in the ST or LT treatment period will be included in summaries of the combined ST+LT treatment periods.

No formal comparisons will be made between treatments. No formal statistical testing will be performed, only summary statistics will be provided.

7.6.2 Deaths

All deaths recorded on the status page, the AE page, or SAE page (with a death date, cause of death, outcome or SAE categorization present) of the CRF will be considered a death in the analyses. Any deaths that occur during the study will be described in depth as narrative in the CSR. A listing of all deaths that occur prior to the start date of long-term treatment period will be produced for ST and listing of all deaths that occur during the study will be produced for ST+LT.

7.6.3 Serious Adverse Events

All SAEs (including hypoglycemic events) will be described in narratives, regardless of investigator assessment of causality.

SAEs with an onset from Day 1 of short-term treatment up to and including 30 days after the last dose date in the short-term treatment period (or up to the start date of the long-term treatment period whichever comes first) will be considered as occurring during the short-term treatment period.

SAEs with an onset from Day 1 of ST treatment up to and including 30 days after the last dose date in the ST or LT treatment period will be considered as occurring during the combined ST+LT treatment periods.

SAEs occurring during the ST/ST+LT treatment period will be summarized by system organ class, preferred term and treatment group for both the primary and sensitivity safety analyses. In addition, the proportion of subjects with related SAEs will be presented by system organ class, preferred term and treatment group.

A listing of all SAEs for ST will be produced, displaying all SAEs (including pre-treatment events) that occurred prior to the start date of long-term treatment period.

A listing of all SAEs for ST+LT will be produced, displaying all SAEs (including pre-treatment events) that occurred during the study.

7.6.4 Adverse Events Leading to Discontinuation of Study Medication

AEs with an onset during the short-term treatment period reported with an action taken of discontinuation of study medication will be summarized by system organ class, preferred term and treatment group for both the primary and sensitivity safety analyses. This summary will include hypoglycemia events that reported as SAEs. AEs leading to discontinuation with an onset date on or prior to the start date of the long-term treatment period will be summarized. In addition, a subject listing of discontinuations due to AEs will be provided, displaying all events that led to discontinuation with an onset date prior to the start of long-term treatment period.

AEs with an onset during the combined ST+LT treatment periods reported with an action taken of discontinuation of study medication will be summarized by SOC, PT, and treatment group for the primary safety analysis. This summary will include hypoglycemia events that reported as SAEs. When summarizing AEs leading to discontinuation for ST+LT, no upper cutoff day windows (ie, 4 days and 30 days from last dosing date for AEs and SAEs respectively) will be applied. In addition, a subject listing of discontinuations due to AEs will be provided, displaying all events that led to discontinuation.

7.6.5 Adverse Events of Special Interest (AEOSI)

Separate summaries will be provided for the following adverse events of special interest (AEOSI). Except as otherwise noted, to identify each type of adverse event of special interest in this section, a list of PTs will be selected before database lock and unblinding of the database.

AEs and SAEs of special interest with an onset from Day 1 of short-term treatment up to and including 4 days and 30 days respectively, after the last dose date in the short-term treatment period (or up to the start date of the long-term treatment period whichever comes first) will be considered as occurring during the short-term treatment period.

AEs and SAEs of special interest with an onset from Day 1 of ST treatment up to and including 4 days and 30 days respectively, after the last dose date in the ST or LT treatment period will be considered as occurring during the combined ST+LT treatment periods.

7.6.5.1 Hypoglycemia

Separate pages to capture events of hypoglycemia are contained within the CRF.

Hypoglycemic events with an onset from Day 1 of the short-term open-label treatment up to and including 4 days after the last dose date in the short-term open-label treatment period (or up to and including the start date of the long-term treatment period, whichever comes first) will be considered as occurring during the Short-term open-label treatment period. Hypoglycemic events with an onset from Day 1 of the short-term open-label treatment up to and including 4 days after the last dose date in the long-term treatment period will be considered as occurring during the Short-term plus long-term treatment period.

Hypoglycemic events will be categorized using two methods. One classification is based on the ADA recommendations²:

Severe hypoglycemia: “An event requiring assistance of another person to actively administer carbohydrate, glucagons, or other resuscitative actions. These episodes may be associated with sufficient neuroglycopenia to induce seizure or coma. Plasma glucose measurements may not be available during such an event, but neurological recovery attributable to the restoration of plasma glucose to normal is considered sufficient evidence that the event was induced by a low plasma glucose concentration.” **Error! Bookmark not defined.**

Documented symptomatic hypoglycemia: “An event during which typical symptoms of hypoglycemia are accompanied by a measured plasma glucose concentration \leq 70mg/dl (3.9mmol/l).” **Error! Bookmark not defined.**

Asymptomatic hypoglycemia: “An event not accompanied by typical symptoms of hypoglycemia but with a measured plasma glucose concentration \leq 70mg/dl (3.9mmol/l). Since the glycemic threshold for activation of glucagon and epinephrine secretion as glucose levels decline is normally 65–70mg/dl (3.6–3.9mmol/l) (24–26) and since antecedent plasma glucose concentrations of \leq 70mg/dl (3.9mmol/l) reduce sympathoadrenal responses to subsequent hypoglycemia (1,11,20), this criterion sets the lower limit for the variation in plasma glucose in nondiabetic, nonpregnant individuals as the conservative lower limit for individuals with diabetes.” **Error! Bookmark not defined.**

Probable symptomatic hypoglycemia: “An event during which symptoms of hypoglycemia are not accompanied by a plasma glucose determination (but that was presumably caused by a plasma glucose concentration \leq 70mg/dl [3.9mmol/l]). Since many people with diabetes choose to treat symptoms with oral carbohydrate without a test of plasma glucose, it is important to recognize these events as “probable” hypoglycemia. Such self-reported episodes that are not confirmed by a contemporaneous low plasma glucose determination may not be suitable outcome measures for clinical studies that are aimed at evaluating therapy, but they should be reported.” **Error! Bookmark not defined.**

Relative hypoglycemia: “An event during which the person with diabetes reports any of the typical symptoms of hypoglycemia, and interprets those as indicative of hypoglycemia, but with a measured plasma glucose concentration $> 70\text{mg/dl}$ (3.9mmol/l). This category reflects the fact that subjects with chronically poor glycemic control can experience symptoms of hypoglycemia at plasma glucose levels $> 70\text{mg/dl}$ (3.9mmol/l) as plasma glucose concentrations decline toward that level (27,28). Though causing distress and interfering with the patient’s sense of well-being, and potentially limiting the achievement of optimal glycemic control, such episodes probably pose no direct harm and therefore may not be a suitable outcome measure for clinical studies that are aimed at evaluating therapy, but they should be reported.” **Error! Bookmark not defined.**

The second classification of hypoglycemic events follows:

Major episodes of hypoglycemia - defined as symptomatic episodes requiring external (3rd party) assistance due to severe impairment in consciousness or behavior with a capillary or plasma glucose value $< 3\text{ mmol/L}$ ($< 54\text{ mg/dL}$) and prompt recovery after glucose or glucagon administration.

Minor episodes of hypoglycemia - defined as either a symptomatic episode with a capillary or plasma glucose measurement below 3.5 mmol/L (63 mg/dL) regardless of need for third-party assistance or an asymptomatic capillary or plasma glucose measurement below 3.5 mmol/L (63 mg/dL), that does not qualify as a major episode.

Other episodes of hypoglycemia - defined as episodes reported by the investigator that are suggestive of hypoglycemia but do not meet the above criteria.

All analyses of hypoglycemic events will be performed both overall and by each class of events both including and excluding rescue data, with the ADA classification system and excluding rescue data analysis serving as the primary analysis. Data collected in the hypoglycemia CRF modules of the CRF will be included in the analysis. All blood glucose measurements collected in the hypoglycemia module of CRF will be considered for classifying the hypoglycemia events irrespective of the method using which glucose data were collected.

The total number of events by treatment group will be summarized for the short-term open-label treatment period. Hypoglycemic events with an onset during the short-term open-label treatment period and leading to discontinuation of study medication will be summarized by treatment group. When summarizing hypoglycemic events leading to discontinuation no upper cutoff day windows are applied. For short-term open-label period analyses the only upper cutoff date is the start date of the long-term treatment period.

A summary of the incidence of confirmed hypoglycemia, defined as blood glucose value $\leq 70\text{mg/dL}$ as recorded in the hypoglycemia module of CRF will be provided.

A listing of subjects will be produced and it will display all hypoglycemic events with an onset date/time from the start date/time of short-term open-label treatment period up to the start date of the long-term treatment period

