6 STUDY PERIODS, TREATMENT REGIMENS AND POPULATIONS FOR ANALYSES

6.1 Study Periods

Study CV181-369 consists of 4 study periods:

- 1) **Screening period (Period A).** This period starts with enrollment (i.e., signature of the protocol-specific informed consent form constitutes the first procedure of the Screening period) and ends on the start of lead-in period. Subjects should be on a stable dose of metformin 1500 mg/day for at least 8 weeks prior to screening visit with or without a stable dose of a SU of at least 50% the maximal dose per local label.
- 2) **Lead-in period (Period B).** During this period, subjects will continue their diabetes management with stable dose of metformin 1500 mg/day with or without a stable dose of SU, diet and exercise. No placebo or study medication will be provided during the lead-in period.
- 3) **24-week short-term open-label treatment period (Period C).** On the Day 1 visit, subjects who meet all the protocol-specific enrollment and randomization criteria will be randomized.
- 4) **28-week long-term open-label treatment period (Period D).** After completing the short-term period, subjects will enter the 28-week open-label long-term treatment period. The start date of long-term treatment period is defined as the end date of short-term treatment period. This is the date when the subject entered the long-term treatment period and was dispensed long-term study medication.

Follow-up non-treatment phase (Period X). Subjects who discontinue study treatment early will follow the same visit schedule as subjects who remain on treatment.

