6.3 Populations for Analyses

6.3.1 *Enrolled Subjects Data Set*

This consists of all subjects who signed informed consent.

6.3.2 *Lead-in Subjects Data Set*

The lead-in subject data set includes data collected from all subjects who have at least one vital sign measurement during Lead-in Period.

6.3.3 *Randomized Subjects Data Set*

The randomized subject data set will consist of all randomized subjects who receive at least one dose of study medication. Whenever using the randomized subject data set, subjects will be presented in the treatment group to which they were randomized at the start of the Short-term treatment Period (even if the treatment they received was different). This is also known as the Intent-to-Treat (ITT) population. This will be the primary efficacy data set.

6.3.4 *Full Analysis Set*

The full analysis set (FAS) is defined as all randomized subjects who take at least one dose of the study medication and have a baseline value for HbA1c. Analysis of the FAS will be based on the randomized treatment.

6.3.5 *Evaluable Subjects Data Set*

The Evaluable Subjects Data Set will be a subset of the Randomized Subjects, with all data points collected after a relevant protocol deviation excluded from the data set. Relevant protocol deviations are defined as deviations that could potentially affect the interpretability of the study results. This is also known as the Per-protocol population. All decisions to exclude patients and/or data from the Randomized Subjects Data Set will be made prior to un-blinding the study and agreed by the study team.

6.3.6 *Treated Subjects Data Set*

The Treated Subjects Data Set for ST and ST+LT will consist of all subjects who receive at least one dose of study medication during the short-term treatment period. This will be the primary safety data set. Data in this data set will be analyzed based on randomized treatment, except in cases where a subject received a different treatment for the entire course of his/her participation in the treatment period. In this case, safety data for such a subject will be analyzed based on the first treatment the subject actually received.

6.3.7 *Short-term Completers Data Set*

The short-term Completers Data Set will consist of all subjects in the Randomized Subjects Data Set who were not rescued, and completed ST treatment and entered the LT treatment period. It is a subset of the Randomized Subjects Data Set.

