8.3.1 Post treatment efficacy and safety evaluations

While efficacy and safety observations will be listed regardless of whether the subject was taking open-label study drug, observations may not contribute to summaries/analyses if they are measured after the last dose of the open-label study medication given during the treatment periods, as indicated below:

For efficacy parameters:

- Lipids and metabolic surrogate markers will be summarized only if measured on or prior to the 4th day after the last study drug treatment date.
- FPG and spot urinary glucose to creatinine ratio will be summarized/analyzed only if measured on or prior to the first day after the last study drug treatment date.
- HbA1c and body weight will be summarized/analyzed only if measured on or prior to the 8th day after the last study drug treatment date.

For safety parameters:

- SAEs and the lab measurements for the liver function tests will be included in the summaries only if occurred/measured on or prior to the 30th day after the last study drug treatment date.
- All other safety events (non-severe AEs, hypoglycemia, etc) and measurements (safety lab, vital signs, etc) will be included in the summaries only if occurred/measured on or prior to the 4th day after the last study drug treatment date.

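### The 52-week hypoglycemia window is tied to the last long-term dose only, so on-treatment events in subjects who stop in the short-term period can be left out of the 52-week results

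*SAP*

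**What the plan says.** SAP Section 7.6.5.1 gives hypoglycemia two windows. The short-term window closes 4 days after the last short-term dose, "or up to and including the start date of the long-term treatment period, whichever comes first". It works for every treated subject. The ST+LT window starts on the same Day 1 but runs "up to and including 4 days after the last dose date in the long-term treatment period will be considered as occurring" in the combined period. It names no alternative for a subject without a long-term dose.

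The other ST+LT safety windows are anchored differently:
- **Section 7.6.1.1 (adverse events):** events up to 4 or 30 days "after the last dose date in the ST or LT treatment period will be included in summaries of the combined ST+LT treatment periods".
- **Section 7.6.5 (events of special interest, the parent of 7.6.5.1):** the same limits "after the last dose date in the ST or LT treatment period will be considered as occurring during the combined ST+LT treatment periods".
- **Sections 7.6.3, 7.6.6 and 7.6.7 (serious adverse events, laboratory data, vital signs):** also the last ST or LT dose.
- **Section 8.3.1 (general convention):** "All other safety events (non-severe AEs, hypoglycemia, etc) and measurements (safety lab, vital signs, etc) will be included in the summaries only if occurred/measured" within a stated limit. That limit, which is not tied to either period, is "on or prior to the 4th day after the last study drug treatment date".

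Section 6.3.6 defines the Treated Subjects Data Set, for both ST and ST+LT, as "all subjects who receive at least one dose of study medication during the short-term treatment period". Section 2.2 takes only subjects who complete the short-term period into the long-term period.

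**The concern.** A subject who stops study drug in the short-term period has no date that satisfies the ST+LT rule, but is still counted in the ST+LT analysis set. If the rule is programmed as written, the comparison with a missing long-term dose date fails and the subject's events are not placed in the combined period. The subject then adds to the denominator and cannot add to the numerator.

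The same event would count in the 24-week proportion and be absent from the 52-week one, in the same analysis set. A cumulative proportion should not lose subjects in this way, and it would fall between the two reports if the loss exceeded the number of new first events in the long-term period.

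The results at stake are exploratory endpoint 9 (confirmed hypoglycemia at Week 52) and the Week 52 hypoglycemia safety endpoint in Section 4.4. Section 1 names hypoglycemia as a main drawback of insulin, so readers will look at the 52-week comparison. If short-term stopping, or hypoglycemia among those who stop, differs between arms, the comparison is biased.

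**Working it through.** No figure in the SAP depends on this window, so there is none to reproduce. The check sets the rules side by side for one hypothetical subject and then sizes the effect under stated assumptions.

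**One subject.** A treated subject has confirmed hypoglycemia at Week 4 and takes the last dose at Week 6.

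| Rule | Anchor date | Does this subject have it? | Result for the event |
|---|---|---|---|
| 7.6.5.1, short-term | last short-term dose | yes | counted at 24 weeks |
| 7.6.5.1, ST+LT | last long-term dose | no | not placed in the 52-week period |
| 7.6.1.1, 7.6.3, 7.6.5, 7.6.6, 7.6.7, ST+LT | last ST or LT dose | yes | would be inside the window |
| 8.3.1 | last study drug date | yes | not barred |

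**Which rule governs?** Section 8.3.1 is a restriction: it says which events may not enter a summary. It does not bring in an event that the specific definition in 7.6.5.1 fails to assign to the period. The windows in 7.6.1.1 and 7.6.5 are worded for adverse events and serious adverse events, and Section 7.6.1 keeps non-serious hypoglycemia off the adverse event page. None of these clearly overrides the specific sentence in 7.6.5.1.

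**Size.** Section 5 plans 299 subjects per arm. Let *d* be the fraction who stop in the short-term period and *h* the fraction of those with an on-treatment event. The SAP gives neither, so both are assumptions: *d* from 5% to 15%, *h* from 10% to 50%.

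Subjects lost from the numerator = 299 × *d* × *h*. Loss in percentage points = 100 × *d* × *h*.

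| *d* | Stop (299 × *d*) | *h* | Subjects lost | Points lost |
|---|---|---|---|---|
| 5% | 15.0 | 10% | 1.5 | 0.5 |
| 5% | 15.0 | 50% | 7.5 | 2.5 |
| 10% | 29.9 | 10% | 3.0 | 1.0 |
| 10% | 29.9 | 50% | 15.0 | 5.0 |
| 15% | 44.9 | 10% | 4.5 | 1.5 |
| 15% | 44.9 | 50% | 22.4 | 7.5 |

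The distortion of the between-arm difference is the difference between the two arms' losses. It is zero if *d* × *h* is equal in both arms. With the last ST or LT dose as anchor, the loss is zero in each arm.

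**The case against.** The strongest reply is that the intent is plain. A period called short-term plus long-term, starting on Day 1 of short-term treatment, cannot sensibly exclude an event that the preceding sentence places in the short-term period. The parent Section 7.6.5 has the ST or LT wording. Section 7.6.1.1 also calls for a summary of all adverse events including hypoglycemia, with similar analyses for ST+LT under that wording. On this view only a programming slip could drop the events. This stands as evidence of intent, but it does not change the text of 7.6.5.1. If that text is followed, the dedicated hypoglycemia tables could also disagree with the all-events summary.

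Four stronger readings are tempting, and the SAP does not support them:

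- **That these subjects have no valid cut-off anywhere.** This is true of the ST+LT sentence in 7.6.5.1 alone. Section 8.3.1 supplies a cut-off that every treated subject has.
- **That months of off-treatment hypoglycemia could be counted.** Section 6.1 says "Subjects who discontinue study treatment early will follow the same visit schedule as subjects who remain on treatment", so later events could be recorded, and a missing date could be coded as no upper limit. But 8.3.1 bars anything after the 4th day from the summaries. For endpoint 9, Section 7.5.1 also excludes values after treatment discontinuation from the main efficacy analyses.
- **That the Week 52 composite endpoints 10 and 15 are affected.** They need an HbA1c response at Week 52. Sections 8.3.1 and 8.5 accept HbA1c only to the 8th day after the last dose, so a short-term stopper should have no usable Week 52 value and should count as a failure under Section 7.1.8, whatever the hypoglycemia window says.
- **That the problem is specific to subjects who stop because of hypoglycemia.** It reaches anyone who stops in the short-term period for any reason and had an event. Short-term hypoglycemia leading to discontinuation has its own summary in 7.6.5.1, without the day limit.

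**Conclusion.** The point holds as an inconsistency. The ST+LT hypoglycemia window in Section 7.6.5.1 departs from the five parallel ST+LT windows and from Section 8.3.1. Taken literally, it can omit on-treatment events of subjects who remain in the denominator.

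Its reach is limited to the 52-week hypoglycemia results: exploratory endpoint 9 and the safety summaries. This takes endpoint 9 to use the period definition in 7.6.5.1, the only ST+LT window written specifically for hypoglycemia. Section 7.5.5 states that exploratory endpoints are not tested, and Section 7.6.1.1 plans no formal testing of adverse events. A reader might infer that the hierarchically tested hypoglycemia endpoint is at risk; it is not, because the 24-week window is properly bounded.

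The loss of about 0.5 to 7.5 percentage points per arm rests entirely on the assumed stopping and event rates, and arises only if the literal rule is programmed.

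**What to change.** In Section 7.6.5.1, change the anchor of the ST+LT window from the last dose in the long-term period to the last dose in the ST or LT period, keeping the 4 days, and add a cross-reference to Section 8.3.1. State that exploratory endpoint 9 uses this window. Endpoints 10 and 15 need no change on this account.

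The cost is one phrase and one cross-reference. No new data are needed, no clinical procedure changes, and the 24-week analysis is untouched. The change should be made before the 52-week tables are programmed.
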